9.7.2 Subgroup and Sensitivity Analyses

Subgroup and sensitivity analyses will be implemented when sample size allows.

Analyses will be presented separately for all participants with PNH, for pregnant female participants with PNH, for all infants, and for infants sub-grouped by breastfeeding status (yes/no).

When feasible, analyses will be further detailed according to each trimester of pregnancy and each quarter within the infant's first year of development.

To account for previous complement inhibitor exposure, subgroup analyses will be also based on previous PNH treatment exposure, using the following definitions: "naïve new users" when individuals initiate crovalimab without prior exposure to C5 inhibitors, and "Prevalent new users" when individuals initiate crovalimab after having received at least one C5 inhibitor any time prior to crovalimab treatment start. Safety events will be also described by causality.

Potential confounding factors influencing safety and pregnancy outcomes, such as demographic information (e.g., age, race/ethnicity), clinical characteristics, maternal medical history, obstetrical history, comorbidities, and concomitant medications will be described among participants with PNH who experience an AESI, as well as for pregnancy or infant outcomes. If needed, subgroup analysis will be performed and AESIs proportions and incidence rates will be compared between subgroups.

Similarly, subgroup analysis may include clinical and laboratory test outcomes for PNH (e.g., MAVEs, HDA, BTH, etc.) and previous PNH treatment.

Sensitivity analysis will be performed restricting the data to safety events and crovalimab exposure that was collected prospectively only. The effects of the timing of crovalimab exposure before and during pregnancy and cumulative exposure periods on each outcome will be also evaluated as sensitivity analysis. Sensitivity analysis may also include timing variations of FTT and development deficiency outcomes, when available.

Full details on all statistical analyses, including other subgroup and sensitivity analyses, will be described in the Statistical Analysis Plan (SAP).

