Analyses will be presented separately for the entire PNH participant cohort, pregnant female participants with PNH, all infants, and infants categorized by breastfeeding status (yes/no). When feasible, these analyses will be further detailed according to each trimester of pregnancy and each quarter within the infant's first year of development. Additionally, where data allows, outcomes will be analyzed based on prior PNH treatment and using the classifications of naïve new users and prevalent new users.

Potential confounding factors influencing safety and pregnancy outcomes, such as demographic information (e.g., age, race/ethnicity), clinical characteristics, maternal medical history, obstetrical history, comorbidities, and concomitant medications will be used in subgroup analyses among participants with PNH who experience an AESI, as well as for pregnancy or infant outcomes. Adverse events of special interest proportions and incidence rates will be compared between subgroups. Similarly, subgroup analysis by clinical and laboratory test outcomes for PNH will be performed when feasible. Safety events will be also described by causality.

Sensitivity analysis will be performed restricting the data to safety events and crovalimab exposure that was collected prospectively only. The effects of the timing of crovalimab exposure before and during pregnancy and cumulative exposure periods on each outcome will be also evaluated as sensitivity analysis. Sensitivity analysis may also include timing variations of failure to thrive (FTT) and development deficiency outcomes, when available.

Full details on all statistical analyses, including other subgroup and sensitivity analyses, will be described in the Statistical Analysis Plan (SAP).

MILESTONES

FIRST DATA EXTRACTION:

The date of first data extraction is the date when the variables used for the data analysis as per protocol are extracted for the first time. The planned first data extraction is after 6 months of Crovalimab Silo inception. The planned first data extraction is in Q1 2026.

LAST DATA EXTRACTION:

The last data extraction is the date of the end of the Crovalimab Silo registry, plus an additional 6 months to account for final data transfer. The planned last data extraction is in Q2 2032.

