- Malignancies and hematologic abnormalities: Long-term immunosuppression may be associated with an increased risk of malignancy, including hematologic and non-hematologic malignancies.
- TICRs: Such immune reactions could occur when patients are switching from eculizumab or ravulizumab to crovalimab (and vice versa), as crovalimab and other C5 inhibitors bind to different epitopes of C5 and can form large drug-target-drug complexes (DTDCs).
- Infusion and injection-related reactions (IRRs): IRRs are considered a risk for all biologic medications, including mAbs, that are administered by intravenous (IV) and/or subcutaneous (SC) routes.
- Use in pregnancy and/or breastfeeding. The safety of crovalimab during pregnancy and breastfeeding is unknown.

To gather more information on the safety profile of crovalimab in a real-world setting, Roche has entered a partnership with the International PNH Interest Group (IPIG), to participate in the existing registry (further referred to as the “Core Registry”, ClinicalTrials.gov ID NCT06524726). A crovalimab sub-registry (further referred to as the “Crovalimab Silo” or Study MO44987) will be established, to enable additional safety data collection in patients with PNH treated with crovalimab. The study described herein (MO45473) is a secondary data use (SDU) study which aims to analyze data from the participants enrolled in the Crovalimab Silo.

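### The prior-treatment subgroups claim to account for complement inhibitor exposure but are defined by C5 inhibitors alone, so prior users of only a non-C5 complement inhibitor are counted as naive

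*Protocol*

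**What the plan says.** Section 9.7.2 of the protocol states the purpose and the basis of the split in one clause: "To account for previous complement inhibitor exposure, subgroup analyses will be also based on previous PNH treatment exposure". Two groups follow. Naive new users are those where "individuals initiate crovalimab without prior exposure to C5 inhibitors". Prevalent new users are those where "individuals initiate crovalimab after having received at least one C5 inhibitor any time prior to crovalimab treatment start". No other category is defined.

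Later in the same section, optional subgroups are mentioned ("e.g., MAVEs, HDA, BTH, etc.) and previous PNH treatment"), without categories for previous treatment. The synopsis (Section 4) says that, where data allow, "outcomes will be analyzed based on prior PNH treatment and using the classifications of" naive and prevalent new users. All subgroup work is conditional on sample size, and Section 9.7.1 rules out formal testing.

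**The concern.** The aim names the whole class of complement inhibitors; the rule that carries it out looks at one subclass. Anyone who previously received only a non-C5 complement inhibitor meets the naive definition despite earlier complement blockade.

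This matters most for risks that the protocol links to the class. Section 7 attributes the risk of serious infection to complement inhibition generally, and serious infection is a primary AESI. A reader of the report would take the naive stratum as showing crovalimab in people never before complement-inhibited, and under this rule it need not be that. The pair is also the only split by prior treatment for which the protocol writes definitions, so those definitions will probably be carried into the outputs as they stand.

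**Working it through.** This is mainly a check of definitions against the stated aim. The protocol gives no figure to reproduce on this point.

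**Step 1. Does the wording differ in substance, or are the two terms interchangeable?**
- Sections 9.2.3 and 9.3.1.1 and the footnotes to Table 1 set post-discontinuation follow-up by whether a new complement inhibitor is started: the wide term.
- Section 9.9.8 speaks of other complement inhibitors in the registry: again the wide term.
- Section 13 lists a paper on C3 inhibition as a strategy in PNH, so complement inhibition other than at C5 appears within the document.
- Section 9.7.2 uses the wide term for its aim and the narrow term for both definitions.

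The terms are therefore not used as synonyms throughout, and the narrower one changes who is counted.

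**Step 2. Can such a participant enter the study?** Section 9.2.2 requires PNH confirmed by flow cytometry, consent, and current or new crovalimab treatment. The one exclusion concerns interventional PNH trials. Prior non-C5 complement inhibition is not excluded.

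**Step 3. Where is that participant placed?** No prior C5 inhibitor means naive. With only two classes there is nowhere else to go.

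**Step 4. Does another provision change this?** The optional subgroup by previous PNH treatment could show these participants separately, but it has no categories and leaves the two definitions as they are.

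**Step 5. How large could the effect be?** The protocol gives no expected number of prior non-C5 users and no risk for them, so the following is illustration only. Let s be the share of the naive group that had only a non-C5 complement inhibitor, RR their risk relative to the truly naive, and p the risk in the truly naive. The reported naive proportion is

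p(1 − s) + p × RR × s.

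I take p = 6%, borrowed from the serious-infection proportion that Section 9.5 quotes from the crovalimab trials (it is not specific to naive participants). I assume s from 5% to 30% and RR from 1.5 to 3:

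| s | RR = 1.5 | RR = 2 | RR = 3 |
|---|---|---|---|
| 0% | 6.0% | 6.0% | 6.0% |
| 5% | 6.15% | 6.3% | 6.6% |
| 10% | 6.3% | 6.6% | 7.2% |
| 20% | 6.6% | 7.2% | 8.4% |
| 30% | 6.9% | 7.8% | 9.6% |

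For example, s = 10% and RR = 2 gives 0.06 × 0.90 + 0.06 × 2 × 0.10 = 0.054 + 0.012 = 6.6%. With s = 0, or with RR = 1, nothing changes; with RR below 1 the reported value would fall.

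**The case against.** The strongest reply is that a C5-based split has a documented reason. Section 7 explains TICR by different C5 inhibitors binding different epitopes: "Such immune reactions could occur when patients are switching from eculizumab or ravulizumab to crovalimab (and vice versa". For TICR, prior C5 exposure is the relevant variable, and the fault could be no more than a loose phrase in the aim. This stands for TICR, and the C5 split should be kept. It does not cover the general aim as written, or class-level risks such as infection.

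A second reply is that the analysis is minor: conditional, descriptive, and one of several. That stands too. A reader might infer that the primary AESI results are compromised. They are not, because Section 9.7.1 pools all participants regardless of this label.

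A third reply is that few participants may be affected. The only existing therapies that Section 7 names are eculizumab and ravulizumab, both treated there as C5 inhibitors. This also stands: the share misfiled is undocumented.

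Two stronger readings are tempting and not supported:
- **That the contrast between naive and prevalent users is necessarily shrunk.** This needs prior non-C5 users to carry a risk close to that of prior C5 users. The protocol gives neither risk, so the direction of any bias is not established.
- **That pooling everyone treated "after having received at least one C5 inhibitor any time prior to crovalimab treatment start" understates TICR risk by a known amount, and that TICR should be analysed only in prior C5 users.** The protocol does not present the prevalent group as direct switchers and gives no share of remote users. Because TICR can also follow a switch from crovalimab to another C5 inhibitor, and follow-up runs 12 weeks into a new complement inhibitor, such a restriction would drop people who are at risk.

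Finally, details may be left to the SAP. But the protocol has already fixed both definitions; the issue is what they say, not that something is absent.

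**Conclusion.** The mismatch is real. Section 9.7.2 sets out to account for prior complement inhibition and classifies by prior C5 inhibition only, so participants previously treated only with a non-C5 complement inhibitor are counted as naive. The consequence is limited to interpretation of a conditional, descriptive subgroup analysis. Its size cannot be derived from the protocol: it is zero if no such participants enrol, and under the assumptions shown the naive serious-infection proportion would move from 6.0% to between 6.15% and 9.6%. The conclusion rests on the definitions, not on those figures. It is worth correcting because the correction is cheap and the label would otherwise mislead.

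**What to change.** Replace the two classes in Section 9.7.2 (and the matching synopsis text) with three, using the previous PNH treatment history already collected under Section 9.3.3:

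1. no prior complement inhibitor of any class, the only group called naive;
2. any prior C5 inhibitor;
3. prior non-C5 complement inhibitor only, reported descriptively, or as a listing if small.

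Optionally, for TICR, describe level 2 further by time since the last C5 inhibitor dose where that date is available, without restricting the TICR analysis to level 2.

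Restating the aim as prior C5 inhibitor exposure would remove the contradiction, but would still leave previously complement-inhibited people under the naive label.

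The cost is mainly wording, and lowest before the first data extraction planned for Q1 2026. There are two downsides. Level 3 may be sparse among about 300 participants. And the dated row in Table 1 covers the last PNH treatment, with an exception for a previous silo drug, so it may not give the last C5 date when the most recent drug was non-C5. The sponsor should confirm that the full treatment history, with dates, reaches the analysis file.

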9.8 QUALITY CONTROL

ICON/IPIG Registry must maintain adequate and accurate records to enable the conduct of the study to be fully documented, including but not limited to the protocol, protocol amendments, Informed Consent Forms (if applicable), and documentation of IRB/IEC and governmental approval (if required).

The MAH shall ensure that the datasets and statistical programs that are held within MAH systems and used for generating the analysis results included in all interim reports and the final study report are kept in electronic format and are available for auditing and inspection.

Data not held within MAH systems will be periodically transferred electronically from ICON/IPIG Registry to the MAH. ICON/IPIG Registry will comply with the MAH procedures regarding content, archiving and records management of process documents, as described in the data transfer agreement.

Retention of Records

Archiving at the study site has to be for at least five years after final study report or first publication of study results, whichever comes later; or according to local regulation.

Records and documents pertaining to the conduct of this SDU study must be retained by the MAH for at least 25 years after completion of the study, or for the length of time required by relevant national or local health authorities, whichever is longer. After that period, the documents may be destroyed, subject to local regulations.

No records may be disposed of without the written approval of the MAH.

Written notification should be provided to the MAH prior to transferring any records to another party or moving them to another location.

9.9 LIMITATIONS OF THE RESEARCH METHODS

This study is a long-term, non-interventional investigation where data collection mirrors routine clinical practice rather than adhering to mandatory assessments at pre-specified intervals. Given the nature of non-interventional studies, long-term follow-up, and the focus on rare diseases, certain limitations are intrinsic to this study design. The IPIG registry incorporates potential mitigation strategies, which are described below.

9.9.1 Selection Bias

To minimize selection bias, clinicians will be instructed to consecutively enroll all consenting participants with PNH who meet the selection criteria, regardless of other factors. However, since participation in the registry is voluntary for both sites and participants, common non-response selection and participation biases may occur, which is typical for this type of observational registry.

9.9.2 Data Collection Bias

The quality of patient data collected in the registry will depend on the source documentation at the sites. To address this, site training and continuous monitoring will be conducted to minimize missing data and enhance the quality of documentation practices. Additionally, automated edit checks and queries in the EDC system will help minimize missing or incorrect data.

9.9.3 Confounding

Confounding arises when treatment effects or disease exposures vary due to another factor. This can be managed using stratification or subgroup analyses in the statistical evaluation.

9.9.4 Loss to Follow-up

Given the maximum follow-up duration of 7 years, the study may experience a significant proportion of discontinued participants. To detect potential biases, the characteristics of these discontinued participants will be compared with those who complete the registry. Specific Concerns for PNH and Pregnancy In parallel, the MAH will explore options to renegotiate with the IPIG registry if needed to extend the study duration, ensuring a minimum five-year follow-up is met for all enrolled participants with PNH and pregnant participants with PNH are included. Likewise, the MAH will investigate alternative approaches for data collection to supplement enrollment if necessary.

Potential confounding factors affecting pregnancy outcomes will be assessed and contextualized, particularly those related to PNH treatment. It is unlikely that participants with PNH who are pregnant will stop crovalimab therapy entirely due to the severity of PNH relapses.

Moreover, existing evidence suggests PNH is associated with certain pregnancy complications and adverse outcomes, indicating that PNH itself may act as a confounder in the relationship between crovalimab and pregnancy-related outcomes evaluated in this study. Residual confounding from unmeasured factors is anticipated, and its impact on study outcomes cannot be predicted.

9.9.5 Data Collection Procedures

Pregnancy, infant, and breastfeeding outcomes will be collected through a passive reporting system during each follow-up visit by the nurse or hematologist.

Consequently, there exists the potential for underreporting, incomplete reporting, and missing data on pregnancy and infant outcomes. With regards to inconsistent, erroneous, or missing data, queries will be generated electronically and sent to the site staff for correction. The identifying information (assigned username, date, and time) will be collected for both the originator of the query and the originator of the data change (if applicable). An audit trail within the system will track all changes made to the data.

As specific interval data collection for pregnancy and infant outcomes is not feasible in a prospective manner, the MAH will ensure that the exact timing of each data point is documented retrospectively and reported, when feasible, for each trimester of pregnancy and each quarter during the infant's first year of development, to enable subgroup analyses.

Additionally, obstetric and neonatal outcome adjudication is not feasible due to the IPIG collaboration's structure, which relies on hematologists for data collection, without teratologist/obstetric/pediatrician involvement.

9.9.6 Size of Target Populations

Given that PNH is linked to certain pregnancy complications and adverse outcomes, the final sample size of the target population for characterizing pregnant and infant outcomes may be small and therefore could pose a limitation. If low sample size is an issue, alternative PNH data sources may be considered for evaluation.

9.9.7 Representativeness

The latest country feasibility assessment indicates that approximately 50% of the planned 300 participants with PNH are expected to be sourced from selected EU countries, with the remaining approximately 50% from non-EU countries (including United States). The inclusion of these countries is intended to contribute to the overall representativeness of the study population for participants with PNH within the EU and other geographical areas.

Importantly, available evidence suggests that the clinical presentation, pathophysiology, and disease course of PNH are largely consistent across geographic regions. Studies such as [Hillmen et al. 2006](#), [Risitano et al. 2014](#), and [Brodsky 2020](#) have shown that participants with PNH globally exhibit comparable disease characteristics, including complement-mediated hemolysis, risk of thrombosis, and bone marrow failure syndromes. While minor regional or ethnic variations in incidence or specific complications exist (e.g., differences in thrombosis rates between Western and Asian populations ([Brodsky 2020](#); [Sakurai et al. 2019](#))), the fundamental disease process remains consistent.

Moreover, the standard of care, including the use of complement inhibitors, is harmonized in many regions due to international clinical guidelines and shared clinical

practices (Risitano et al. 2014), further supporting the extrapolation of study results across countries.

Consequently, it is expected that participants with PNH receiving crovalimab will share broadly similar demographic and clinical profiles regardless of country of origin (Dingli et al. 2023). Nonetheless, the MAH acknowledges that enrolling participants with PNH from a limited number of countries within each region may present some limitations in terms of generalizability to the entire EU or global PNH population. These limitations will be carefully considered in the analysis and interpretation of the study results.

9.9.8 Lack of comparator safety data

A key limitation of this observational study is our inability to compare crovalimab's safety data directly with the safety data from other complement inhibitors within the IPIG registry. This is due to the study's design and the restrictions of the IPIG registry's data-sharing agreements, which prevent access to and comparison with data from different silos and therefore the inclusion of a dedicated comparator arm.

9.10 OTHER ASPECTS

As the current study is observational, Awareness and Outreach Strategy and Retention Plans are not being implemented by the MAH. Instead, the International PNH Interest Group (IPIG) will manage these activities for the primary data collection on the Silo and Core registries. IPIG is actively promoting the IPIG PNH Registry at the IPIG annual conferences to reach a broad audience of hematologists. Additionally, hematologists will be directly contacted to encourage their participation in the registry and subsequent enrollment of eligible participants with PNH. To support this primary data collection, a comprehensive retention plan will be developed and implemented. This plan will ensure ongoing site and patient engagement through regular communication, provision of study updates, and facilitated data submission, thereby minimizing attrition and maximizing data completeness.

10. PROTECTION OF HUMAN SUBJECTS

10.1 INFORMED CONSENT

The IPIG sample Informed Consent Form (and ancillary sample Informed Consent Forms such as a Child's Assent or Caregiver's Informed Consent Form, if applicable) will be provided to each site in the Crovalimab Silo. If applicable, it will be provided in a certified translation to the local language. The MAH must review and approve any proposed deviations from the IPIG's sample Informed Consent Forms or any alternate Consent Forms proposed by the site (collectively, the "Consent Forms") before IRB/IEC submission. The final Consent Forms approved by the IRB/IEC must be provided to the marketing authorization holder for archiving and for health authority submission purposes according to local requirements.

The Consent Forms must be signed and dated by the patient or the patient's legally authorized representative before the start of extraction of his or her data in the eCRF.

By signing the form, the patient confirms that he/she has been informed about the study and agrees to the secondary use of his/her data, pooling of data with similar scientific data (if applicable), and the possibility of monitoring activities. It is the accountability of the physician for ascertaining that the subject has comprehended the information and to obtain written informed consent from each patient participating in the study. A copy of each signed Consent Form must be provided to the patient or the patient's legally authorized representative. All signed and dated Consent Forms must remain in each patient's study file or in the site file and must be available for verification by Site Operations Representative at any time.

The participants have explicitly agreed to any secondary use of their data.

For this study, it is not necessary, or possible/practical to obtain informed consent for use of secondary data. However certain precautions will be taken, including:

- Ensuring data are pseudonymized
- Ensuring final analysis data are pseudonymized
- Ensuring possibility of linkage back to individual identified participants is impossible or tightly controlled
- Obtaining ethical committee approval for use of data as proposed (e.g., the review of and extraction of information from individual medical charts) for the proposed use ahead of study initiation

